1.1 Background and Significance

Nearly 90 million Americans are obese. To combat obesity and its myriad comorbidities, annually almost 200,000 Americans undergo bariatric surgery, the most effective treatment for obesity. Of contemporary procedures, Roux-en-Y Gastric Bypass (RYGB) achieves the greatest weight loss - between one and two years following RYGB, patients tend to have lost over 30% total body weight. However, the majority of patients regain weight following a two-year nadir [1]. As time from surgery increases, so does the amount of weight regained. Some have reported that more than a third of patients no longer manifest loss of more than 50% pre-surgical excess body weight by ten years after surgery [2]. Weight regain after RYGB is associated with the return of obesity-related comorbidies initially resolved following surgery [3]. Many patients opt for revisional bariatric surgery to address weight regain, but these procedures are often the source of significant morbidity [4, 5]. There are currently few non-surgical therapies with which to address inadequate weight loss and weight regain after bariatric surgery, and these are of limited efficacy.

The use of GLP-1 agonists holds great promise for this population, which likely numbers in the hundreds of thousands in the United States alone. GLP-1 agonist use has been associated with weight loss in diabetic populations, with a meta-analysis finding an average loss of 3% total body weight with GLP-1 receptor agonists versus placebo [6]. Further, several recent randomized trials have demonstrated the efficacy of a specific GLP-1 receptor agonist, liraglutide 3.0mg daily, for the purpose of weight loss. In a study of overweight and obese subjects who first completed a low calorie diet, Wadden and colleagues reported 6.2% weight loss at 56 weeks versus 0.2% with placebo [7]. Another recent trial in over 3,500 overweight and obese patients randomized to liraglutide or placebo, in addition to lifestyle interventions, demonstrated 8.0% weight loss in the liraglutide arm versus 2.6% in the placebo group [8]. Neither of the above randomized trials included overweight or obese patients who had previously undergone bariatric surgery. Although the use of a GLP-1 receptor agonist as an adjuvant to bariatric surgery for weight loss has shown promise in animal models, this therapy has yet to be tested in humans [9].

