5.6 Method for Assigning Subjects to Treatment Groups and Dispensing of Study Drug

5.6.1 Randomization Process

- Eligible subjects will be randomized to one of the two treatment groups in a 2:1 ratio to receive either
- study drug (Liraglutide (rDNA origin) injection, 3 x Saxenda® pen, NDC 0169-2800-13) or matching
- placebo, with stratification by gender and percent post-operative TBWL (<25%, 25 49.9%). Stratified
- block randomization will be employed. Randomization lists will be sent to the pharmacist who will then
- be able to distribute the study drug/placebo as patients are enrolled, and the remainder of the study staff

will be blinded.

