
Blood Pregnancy (Total Beta Quantitative HCG) (Only applicable for women of childbearing

882

883

potential)

- 884 **BMP**
- 885 HbA1c
- Lipid profile 886
- 887 Amylase
- Lipase 888
- 889 Additional 15 ml blood for future analyses - Banking of additional plasma and serum for future markers of caridometabolic risk in post-RYGB patients (6 and 12 months only). 890

891 6.2.5 **Questionnaires**

- 892 PHO-9
- 893 **IPAQ**

894 6.2.6 **Adverse Events Assessment**

- 895 Through-out the study the occurrence of drug-related AEs and pregnancies will be monitored, recorded,
- and reported to IRB and Novo Nordisk. 896

897 **Monthly Contact** 6.2.7

- 898 Study staff will call or email each subject at 1, 2, 4, 5, 7, 8, 10, and 11 months to review medication compliance and 899 adverse events.
 - 7 Statistical Plan

7.1 **Sample Size Determination**

We intend to recruit 132 subjects. A recent study of liraglutide versus placebo in subjects weighing 106.2 \pm +/- 21.1 kg (BMI 38.2 \pm 6.4) at baseline demonstrated that nearly 2/3 of subjects treated with liraglutide for 56 weeks lost at least 5% of enrollment body weight, vs. approximately 1/4 with placebo. We expect to see similar results in our subjects. In order to detect an absolute difference of 36.1% in the proportion of subjects losing at least 5% of enrollment body weight in the liraglutide (expected proportion 63.2%) and placebo arms (expected proportion 27.1%), with an alpha of 0.05 and beta of 0.1, we will require a sample size of 99 (2x liraglutide: 1x placebo). In order to account for an estimated loss-to-follow-up of 25%, we increase the sample size to 132.

7.2 **Statistical Methods**

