Data will be analysed on an intention-to-treat basis. Missing values will be assessed for patterns and imputed using a multiple imputation method for measurements made after baseline. Patient demographics will be summarized by treatment group. Categorical variables will be presented as proportions, normally distributed continuous variables will be presented as mean \pm standard deviation, and skewed continuous variables will be presented as median [interquartile range]. Our primary outcome (proportion of subjects losing at least 5% enrollment body weight) will be assessed using Cochran-Mantel-Haenszel test after accounting for stratification variables. The treatment groups will be further compared by secondary outcomes, using t-tests or Wilcoxon rank sum tests, (as appropriate) for continuous variables. Prior to analysis, non-normally distributed continuous data will be categorized using quartiles or using an appropriate transformation method (e.g. log-transformed).

920 921 922

923

924 925

926

900

901

902

903 904

905

906 907

908

909

910

911 912

913

914

915

916

917

918

919

Paired sample t-tests assessing change at 6 months and 12 months will be used to test, separately for each treatment group, whether each of the post-intervention measurements differs from the baseline measurement. Change in continuous secondary outcome variables will be compared between treatment groups using independent samples t-tests. An ANCOVA model including stratification variables (gender, percent post-operative weight loss) will be used to assess changes in these secondary outcomes. These

927 928	results will provide information to inform further studies, but will remain descriptive given our limited power.
929 930	7.3 Subject Population(s) for AnalysisPrimary and secondary analyses will be performed in the all-treated population.
024	7.4 Interim Analysis
931 932	7.4 Interim Analysis Given the limited duration of the study, we do not plan interim analyses of efficacy parameters.
933	8 Safety and Adverse Events
934	8.1 Definitions
935	8.1.1 Unanticipated Problems Involving Risk to Subjects or Others
936	Any incident, experience, or outcome that meets all of the following criteria:
937	 Unexpected in nature, severity, or frequency

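### Under 2:1 allocation, section 7.2 should name unequal-variance methods for the continuous secondary outcomes: the t-test form is unstated and an ordinary ANCOVA pools one variance

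*Combined protocol and SAP*

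**What the plan says.** Section 7.2 (Statistical Methods) compares change in continuous secondary outcomes between treatment "groups using independent samples t-tests". It then names a second analysis of the same changes: "An ANCOVA model including stratification variables", the variables being gender and percent post-operative weight loss. No variance form is stated for the t-test and no standard error for the ANCOVA. The same section also allows Wilcoxon rank sum tests, and transformation or quartile categories for non-normal data. It describes the secondary results as descriptive because power is limited.

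Section 5.6.1 fixes the allocation: "Eligible subjects will be randomized to one of the two treatment groups in a 2:1 ratio". Section 7.1 carries it into the sample size: "we will require a sample size of 99 (2x liraglutide: 1x placebo", raised to 132 for 25% loss to follow-up.

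Sections 3.2 and 3.6 list the secondary endpoints: fasting glucose, HbA1c, LDL and HDL cholesterol, triglycerides, waist circumference, blood pressure, STOP-BANG and PHQ-9, with a comorbidity assessment added in 3.6. No SD of change is given for any of them in either arm.

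**The concern.** A pooled standard error takes most of its variance estimate from the larger arm, while most of the uncertainty in the difference comes from the smaller arm. With equal arms the two effects nearly cancel. With twice as many patients on liraglutide they do not.

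If change varies more on liraglutide, the standard error is too large and real differences are missed. If it varies more on placebo, the standard error is too small and false positives exceed 5%. Section 3.1 states directional hypotheses for lipids, HbA1c, waist circumference and PHQ-9, so these comparisons will be read as evidence. For the t-test, the silence also leaves the choice between pooled and unequal-variance forms open until the data are in hand.

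**Working it through.** **1. Arm sizes, from the plan's own sample size.** Inputs from section 7.1: 63.2% and 27.1% responders, and error rates "with an alpha of 0.05 and beta of 0.1". Take a two-sided test and ratio r = 2. The pooled proportion is (0.271 + 2 × 0.632)/3 = 0.512.

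- Placebo n = [1.960 √(1.5 × 0.512 × 0.488) + 1.282 √(0.271 × 0.729 + 0.632 × 0.368/2)]² / 0.361² = 28.2.
- With continuity correction: (28.2/4) × [1 + √(1 + 2 × 3/(28.2 × 2 × 0.361))]² = 32.2, rounded up to 33.
- Total 3 × 33 = 99, and 99/0.75 = 132.

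The plan's figures reproduce. The arms are 66:33 evaluable and 88:44 randomised.

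**2. What pooling does to the standard error.** Let q be the SD of change on liraglutide divided by that on placebo.

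- True variance of the difference: s_L²/n_L + s_P²/n_P.
- Pooled version, in large samples: s_L²/n_P + s_P²/n_L. The arm sizes have changed places.
- With n_L = 2n_P, the ratio of pooled to true standard error is k = √[(2q² + 1)/(q² + 2)].

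Example, q = 2: √(9/6) = 1.225, so the standard error is about 23% too large. Example, q = 0.67: √(1.898/2.449) = 0.880, so it is about 12% too small.

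**3. Type I error.** In large samples this is 2[1 − Φ(1.96k)]. I checked it by simulation with normal data (200,000 trials per setting).

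| q | k | Formula | Pooled t, simulated (66:33 / 88:44) | Welch, simulated (66:33 / 88:44) |
|---|---|---|---|---|
| 0.67 | 0.880 | 8.5% | 8.5% / 8.3% | 5.1% / 4.9% |
| 0.8 | 0.929 | 6.9% | 6.9% / 6.9% | 5.0% / 5.0% |
| 1.0 | 1.000 | 5.0% | 5.0% / 5.0% | 5.1% / 4.9% |
| 1.25 | 1.076 | 3.5% | 3.5% / 3.4% | 5.0% / 4.9% |
| 1.5 | 1.138 | 2.6% | 2.7% / 2.6% | 5.0% / 5.0% |
| 2.0 | 1.225 | 1.6% | 1.7% / 1.7% | 5.0% / 5.1% |

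A nominal 95% interval therefore covers about 91.6% at q = 0.67 and 93.1% at q = 0.8.

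**4. Power when liraglutide varies more.** For a difference that Welch detects with 80% power, pooled power is about Φ(2.802 − 1.96k). That is 76%, 72% and 66% at q = 1.25, 1.5 and 2.0.

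**5. ANCOVA.** I simulated 20,000 trials per setting with two binary covariates (prevalence 20% and 50%, assumed) and an assumed continuous baseline.

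- Ordinary standard errors: type I error 8.3% to 8.4% at q = 0.67, 2.7% to 2.9% at 1.5, and 1.7% at 2.0.
- HC3 standard errors: 4.3% to 4.9% over the same settings.

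**6. Cost if the variances are equal.** At 80% power for the pooled t-test, Welch gives 79.6% (66:33) and 79.8% (88:44). For the ANCOVA with HC3 the loss is about 1 point.

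**The case against.** **The plan does not commit to pooling in the t-test.** This stands. Welch's test is also an independent samples t-test, so on this method the plan is silent rather than wrong. The ANCOVA is different: run in its ordinary form, it does pool.

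**Not every secondary p-value is exposed.** This also stands. The error needs both a pooled method and unequal spread. Outcomes analysed by Wilcoxon test or in quartile categories do not use a pooled t-test, and a log transformation may reduce a difference in spread. These routes answer non-normality, though. None is offered as a safeguard against unequal variances.

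**A reader might infer from the plan's own figures that the spreads will differ.** Section 1.1 cites "8.0% weight loss in the liraglutide arm versus 2.6% in the placebo group". Pairing those means with the 63.2% and 27.1% responder rates under normality gives SDs of (8.0 − 5)/0.337 = 8.9 and (5 − 2.6)/0.610 = 3.9, a ratio of about 2.3. The documents do not support this reading, for three reasons.

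- Percent weight change is not a listed secondary endpoint.
- Section 7.1 does not tie the responder rates to those means. Section 1.1 also cites a trial with 6.2% against 0.2%, which gives 1.2/0.337 = 3.6 and 4.8/0.610 = 7.9, a ratio of 0.45 in the opposite direction.
- Normality is assumed. One common SD of 5.9 with right skew of 1.44 (shifted gamma) reproduces both responder rates from the 8.0% and 2.6% means.

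**The results are descriptive, and the primary test, sample size and safety analyses are untouched.** This is true and limits the weight of the point. But the plan wants these results to inform later studies, and the label does not correct a standard error of the wrong size.

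**Conclusion.** The point holds conditionally. If the arms differ in spread, the ordinary ANCOVA and any pooled t-test give wrong standard errors under 2:1 allocation. For SD ratios from 0.67 to 2.0, a nominal 5% test runs at between about 8.4% and 1.7%. The ratios are assumptions, and the documents indicate neither their size nor their direction. The error rates also assume normal data and 66:33 or 88:44 analysed. The primary Cochran-Mantel-Haenszel comparison does not depend on any of this. The consequence is modest, and the change is best classed as a cheap improvement: it is worth making because the replacement methods hold close to their nominal level whichever arm varies more.

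**What to change.** In section 7.2:

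- State that between-arm t-tests on continuous secondary outcomes are Welch (unequal-variance) tests with Satterthwaite degrees of freedom, used in all cases without a preliminary test of equal variances.
- State that the ANCOVA treatment effect is reported with heteroscedasticity-consistent standard errors and a 95% confidence interval. HC3 is one suitable choice at these sample sizes; other consistent estimators are defensible if named in advance.
- Report the SD of change by arm for each outcome, so that readers can see whether the spreads differed.

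This is about one sentence of text and a software option. If the variances turn out equal, the price is under half a point of power for the t-test and about one point for the ANCOVA. Sample size, randomisation and the primary analysis do not change.

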
516517

We hypothesize that the liraglutide group will demonstrate greater improvement

in cardiovascular risk profile (as assessed by serum lipids, HbA1c, and waist

518	circumference) and quality of life (as assessed by the PHQ-9) at 12 months, than
519	the placebo group.
520	 To evaluate the safety of liraglutide in post-RYGB subjects.
521	o We will monitor adverse events, blood counts and serum chemistries in subjects
522	receiving liraglutide or placebo over a period of 12 months.
523	We hypothesize that the liraglutide group will exhibit more frequent
524	hypoglycemia and elevations in lipase and amylase, but that these episodes will
525	be clinically insignificant.
526	• To evaluate the changes in obesity-related comorbid conditions in patients who are experiencing
527	weight regain following RYGB.
528	 We will monitor obesity-related comorbid conditions in subjects receiving liraglutide or
529	placebo over a period of 12 months.
530	 We hypothesize that the liraglutide group will exhibit improvements in obesity-
531	related comorbid conditions (hyperglycemia, hyperlipidemia, blood pressure, and
532	obstructive sleep apnea) at 12 months, than the placebo group.
533	3.2 Endpoints
534	• Primary Endpoint: Proportion of subjects losing at least 5% of enrollment body weight at 12 months.
535	• Secondary Endpoints: Fasting serum glucose, HbA1c, LDL-cholesterol, HDL-cholesterol,
536	triglycerides, waist circumference, blood pressure, STOP-BANG score, PHQ-9
37	• Primary and secondary endpoints will be assessed at clinic visits prior to randomization and at 3, 6, 9
538	and 12 months post-first study drug administration.
539	3.3 Study Type
540	Randomized, single-center, double-blind, placebo-controlled study with two arms. Randomization will
541	be 2:1 (drug:placebo) with stratification by gender and percent post-operative TBWL (25%, 25 – 49.9%).
542	3.4 Rationale for study Design
543	A randomized, placebo-controlled study design was chosen as this is the methodology that will best
544	assess the efficacy of liraglutide for weight loss in the post-RYGB population. 2:1 randomization was
545 546	chosen with the intention of increasing potential participant interest given better than even odds of
547	randomization to liraglutide.
548	A single-center study was chosen given that the NYU Langone weight management program has a pool
549	of 700 post-RYGB patients in our retrospective database, and that recent data from our program suggests

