550	that 80 % of patients at least 18 months status-post RYGB exhibit regain of ≥10% of maximum post-
551	surgical TBWL – our program has a potential subject pool of 560. We estimate that at least 50% of 560
552	will be eligible for and agree to participate in the study, which will allow us to be able to enroll adequate
553 554	subjects from our program alone. In addition, approximately five post-RYGB patients are referred to our program monthly for evaluation of weight regain. In the case that subject recruitment falls short of goals,
555	we would expand recruitment using advertisements.
556	3.5 Primary Study Endpoints
557	Proportion of subjects losing at least 5% of enrollment body weight at 12 months.
	-r

Universal Trial Number: U1111-1178-7319 Version 7: 10/11/2019 Page 15

557

558	3.6 Secondary Study Endpoints
559 560 561	Fasting serum glucose, HbA1c, LDL-cholesterol, HDL-cholesterol, triglycerides, waist circumference, blood pressure, STOP-BANG score, PHQ-9, Obesity-related co-morbidities assessment
562 563	Primary and secondary endpoints will be assessed prior to randomization and at clinic visits at 3, 6, 9 and 12 months post-first treatment administration.
564	3.7 Primary Safety Endpoints
565 566	The primary safety endpoint is the percentage of patients who are experiencing AEs during 12 months of the trial.
567 568 569 570 571 572 573 574	 3.7.1 Assessments for Safety BMP (Fasting glucose) Amylase Lipase Pregnancy Test (Only applicable for women of childbearing potential) Heart Rate PHQ-9 Current medication list review
575	• Adverse event assessment including symptomatic hypoglycaemia for Type 2 DM patients
576	4 Subject Selection and Withdrawal
577 578	4.1 Number of the subjects: 132 Subjects will not be replaced if they withdraw or become ineligible.

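### Section 7.2 names no lead between-arm analysis for the continuous secondary outcomes and does not name each outcome's own baseline value as a covariate; doing both would usually narrow the intervals

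*Combined protocol and SAP*

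**What the plan says.** All the relevant analysis text is in section 7.2, Statistical Methods. Its first paragraph says: "The treatment groups will be further compared by secondary outcomes, using t-tests or Wilcoxon rank sum tests, (as appropriate) for continuous variables". It does not say whether these tests are run on the follow-up value or on the change. It adds that "non-normally distributed continuous data will be categorized using quartiles or using an appropriate transformation method".

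The second paragraph gives within-arm tests ("Paired sample t-tests assessing change at 6 months and 12 months") and then two between-arm analyses of change. One is unadjusted: "Change in continuous secondary outcome variables will be compared between treatment groups using independent samples t-tests". The other is the model: "An ANCOVA model including stratification variables (gender, percent post-operative weight loss) will be used to assess changes in these secondary outcomes". No route is called the main one.

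The paragraph closes by limiting what the results are for: these "results will provide information to inform further studies, but will remain descriptive given our limited power".

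Baseline values will exist. Section 3.6 states: "Primary and secondary endpoints will be assessed prior to randomization", and the visit table in section 6 marks the vital signs, waist, laboratory tests, PHQ-9 and STOP-BANG at baseline. The secondary hypotheses in section 3.1 are stated at 12 months.

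**The concern.** The plan has a baseline measurement of every secondary outcome, yet the only covariates it names are the two stratification factors. Gender and percent post-operative weight loss do not stand in for a subject's own starting HbA1c, lipids, waist, blood pressure or PHQ-9. Subtracting baseline is not the same as adjusting for it: a change score fixes the slope on baseline at 1, whereas ANCOVA estimates it.

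The plan itself gives limited power as the reason to treat these results as descriptive. The estimate and its interval are then what readers will use, so interval width matters. The listed analyses will also give somewhat different estimates for the same outcome, because each handles chance baseline imbalance differently, and the plan does not say which one to read.

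**Working it through.** **1. The plan's own figure.** Section 7.1 gives 63.2% versus 27.1%, alpha 0.05, beta 0.1 and 2:1 allocation. Take the two-sided test of two proportions (sidedness is not stated). The pooled proportion is (0.271 + 2 × 0.632)/3 = 0.5117. The placebo arm needs [1.960 × √(1.5 × 0.5117 × 0.4883) + 1.2816 × √(0.271 × 0.729 + 0.632 × 0.368/2)]² / 0.361² = 28.2. The continuity correction raises this to 33, so the total is 3 × 33 = 99, and 99/0.75 = 132. Both stated figures reproduce. They concern the binary primary endpoint and do not depend on anything below. Section 7.1 gives no SD, correlation or power for the secondary outcomes.

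**2. Assumptions.** Baseline-to-follow-up correlation r = 0.3 to 0.9; baseline SD 1 and follow-up SD k (k = 1 unless stated); a common baseline slope in both arms; strata unrelated to change; complete data on 66 versus 33. None of r, k or the slopes is in the documents.

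**3. Variance per subject.**
- Change score: k² + 1 − 2rk
- ANCOVA with baseline: k²(1 − r²)
- Change minus ANCOVA: (1 − rk)², which is never negative and is zero when rk = 1

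At k = 1 the ratio of ANCOVA to change is (1 − r²)/(2(1 − r)) = (1 + r)/2.

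**4. Interval half-widths.** With √(1/66 + 1/33) = 0.2132 and t = 1.985 on 97 df, the half-width is 0.4231 × √variance, in outcome SDs.

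| r | Change variance | ANCOVA variance | Ratio | Change half-width | ANCOVA half-width | Narrower by |
|---|---|---|---|---|---|---|
| 0.3 | 1.40 | 0.91 | 0.65 | 0.501 | 0.404 | 19% |
| 0.5 | 1.00 | 0.75 | 0.75 | 0.423 | 0.366 | 13% |
| 0.7 | 0.60 | 0.51 | 0.85 | 0.328 | 0.302 | 8% |
| 0.9 | 0.20 | 0.19 | 0.95 | 0.189 | 0.184 | 2.5% |

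**5. The strata-only ANCOVA.** A simulation at 66/33 (4,000 trials per setting, k = 1) compared ANCOVA of change on the strata alone with the same model plus baseline. Mean half-widths were 0.504/0.427/0.331/0.191 without baseline and 0.408/0.371/0.307/0.187 with it, at r = 0.3/0.5/0.7/0.9. Coverage was close to 95% for both. So the strata-only model behaves like the change-score t-test, and both are valid.

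**6. SD ratio.** At k = 0.8 the interval is 29/24/21/22% narrower over the same r; at k = 1.25, 11/5.5/1/2.5%. At r = 0.8 and k = 1.25, rk = 1 and there is no gain.

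**7. Unequal slopes.** With 2:1 allocation, the common slope that ANCOVA fits is weighted toward the larger arm. Take slopes 0.5 (liraglutide) and 1.1 (placebo) with residual SD 0.5. The fitted slope is (66 × 0.5 + 33 × 1.1)/99 = 0.7.
- ANCOVA: (0.25 + 0.2²)/66 + (0.25 + 0.4²)/33 = 0.01682
- Change: (0.25 + 0.5²)/66 + (0.25 + 0.1²)/33 = 0.01545
- Standard error ratio: √(0.01682/0.01545) = 1.04

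Here ANCOVA is about 4% worse. At slopes 0.7 and 1.0 the two are equal.

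**8. How far the estimates drift apart.** Chance baseline imbalance has SD 0.213. At k = 1 the change and ANCOVA estimates differ by (1 − r) times the imbalance, with SD 0.149/0.107/0.064/0.021 outcome SD (slope taken as known). If the first-paragraph t-test is on follow-up values, its estimate differs from the change estimate by the imbalance itself, SD 0.213.

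**The case against.** The case against is substantial. The planned tests are valid, the results are declared descriptive, and no confirmatory secondary claim rests on them. The word *including* does not close the covariate list. If gender and weight-loss band both enter as factors, the label ANCOVA fits better with a continuous covariate such as baseline in mind. The t-test on change in the second paragraph may simply specify the t-test in the first, so the number of distinct analyses is uncertain, and the follow-up-value figure in step 8 depends on a reading that the text does not confirm. The gain rests on assumed correlations and is small when r is high.

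All of that stands, and it keeps the point optional. It does not remove it. The unadjusted t-test on change is planned outright, whatever the ANCOVA was meant to contain, and limited power is a reason to take precision that is already in the data.

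A reader might infer more than the documents support:

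- *That baseline will be left out.* The text does not name it; it does not exclude it.
- *That listing several analyses is an error.* On the untransformed scale, the t-tests and ANCOVA target the same mean difference under randomization.
- *That all the listed routes answer one question.* Wilcoxon tests, log-scale analyses and quartile categories do not estimate that mean difference.
- *That baseline adjustment can never lose.* That needs similar slopes in the two arms; step 7 shows an edge case where it fails.

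**Conclusion.** The point holds as an optional improvement in precision and clarity. Section 7.2 names neither a lead between-arm analysis nor the outcome's own baseline as a covariate. With a common slope, equal SDs and complete data on 66 versus 33, naming baseline narrows the interval by about 19% at r = 0.3, falling to 2.5% at r = 0.9. The gain vanishes where r times the SD ratio equals 1 and can turn into a slight loss when slopes differ greatly. The plan will impute missing values, so realized widths will differ from these complete-data figures.

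It would go too far to conclude that the secondary comparisons are biased or invalid, or that the primary test or sample size needs to change.

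**What to change.** Before unblinding, state in section 7.2 that:

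- the lead between-arm analysis of each continuous secondary outcome is an ANCOVA of the 12-month value on arm, that outcome's baseline value, gender and TBWL stratum, fitted in each imputed dataset and pooled, with the same model at 6 months;
- skewed, strictly positive outcomes (for example triglycerides) are log-transformed at both baseline and follow-up and reported as ratios;
- bounded scores or scores that can be zero (PHQ-9, STOP-BANG) use the same baseline-adjusted model with robust standard errors, with the Wilcoxon test as a supportive check;
- quartile categorization is not used in the lead analysis, and the t-tests are supportive.

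The cost is one degree of freedom (about 1% in variance at N = 99) and SAP wording. No new data, visits or subjects are needed. The amendment goes through the IRB (section 11) and the DSMB (section 8.6.1.4).
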